Figure shows experimental procedure for measurement of rectal compliance by ascending method of limits (AML), sensation thresholds (indicated by arrows) and sensation ratings by random order pressure distensions and recording symptoms using 100mm visual analog scales

Ascending method of limits: compliance and sensory thresholds

Rectal sensory thresholds and compliance are measured by ramp inflation, increasing in steps of 4 mm Hg for 1 minute per step from 0 to a maximum 60 mm Hg. Thresholds for gas, first desire to defecate, urgency, and pain are indicated by the study participants by pressing a button at the distension pressure at which sensations are perceived. Ramp inflation is

terminated as soon as participants reported the first sensation of pain.

The bag is deflated and BOP is determined by pressure in the bag increased from 4 mm Hg in steps of 2 mm Hg for 1 minute per step until respiratory excursions are observed. The baseline operating pressure (BOP) set 2 mm Hg above the minimal distension pressure at which respiratory excursions are clearly recorded from the barostat tracing. Once BOP is determined there is another rest for 10 minutes.

Random order phasic distensions: sensory ratings

Phasic distensions of 12, 24, 30 and 36 mm Hg above BOP are each applied once in random order, (the order being provided before the start of the study by the biostatistician), with the participants blinded to the distension order. Each distention is maintained for 60 seconds with an interval between distensions of 2 minutes with the balloon deflated to BOP. Distension pressure is associated with intensity ratings that are generally proportional to the magnitude of the distension pressures.⁵²⁻⁵⁴ Participants mark three separate 100 mm visual analog scales (VAS) 30 seconds after the onset of the distension for the sensations of gas, urgency, and pain. These scales are anchored at each end by the descriptions 'unnoticeable' and 'unbearable'. Pressure is immediately released if the participant reported greater than 80 mm of pain on the VAS scale and higher distensions are not subsequently administered. During the assessment of sensation, the interaction between the participant and the study investigator is kept to a

minimum. Participants will also complete another VAS questionnaire to describe their sense of tiredness, peace, worry and activity before the first measurement of sensation.

Data analysis for compliance and sensory endpoints

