A “time to event” approach (i.e. pressure required to evoke specific sensations) will be used to assess four sensation thresholds (first desire to defecate, gas, urgency, and pain). Since some threshold levels are “censored” (e.g. pain not evoked by the maximum distension pressure used according to the protocol approved by the IRB), a Kaplan-Meier summary of the pressure thresholds will be used to univariately depict the cumulative probability of evoking the sensation, and proportional hazards regression models will be used to assess group effects separately for each of the sensation types. The same covariates listed above used in the analyses of sensation VAS ratings will be included in the proportional hazards regression models, in particular the ratings of “tiredness”, “peace”, “worried”, and “activity” recorded during the sensation studies.

Rectal compliance

The covariates included in the ANCOVA models for fasting colonic tone and compliance $Pr \frac{1}{2}$ values will be age, gender, BMI, the “tiredness”, “peace”, “worried”, and “activity” scores, the HAD scores, and the BDQ somatic symptom score.

Endpoints

Primary Endpoint

is abdominal pain scores in participants with non-constipation IBS

Summary of Secondary Endpoints will be focused on characterizing rectal compliance and sensation, and colonic transit,

The *secondary endpoints* for analysis will be:

- a. Colonic transit geometric center at 24 hours
- b. Colonic transit geometric center at 48 hours
- c. Gastric emptying of solids $T_{1/2}$ (minutes) and % emptied at 4h
- d. Rectal compliance
- e. Rectal sensation during ascending method of limits
- f. Rectal sensation during random order, graded phasic distensions
- g. IBS-QOL
- h. Safety/adverse effects

Sample Size

This study is meant to be a pilot study that will provide preliminary information regarding the usefulness of treating participants chronic abdominal pain associated with non-constipation IBS with rimegepant.

The estimated effect size (with $n=12$ per treatment group) for each of the primary and secondary endpoints is based on power calculation using data acquired from patients with IBS-D at Mayo Clinic^{56, 57}.

Table 4. Key Gastrointestinal Physiologic Data in 163 People Based on Bowel Function Subgroup

	Healthy controls	IBS-C	IBS-D	IBS-M
Number of males	41 (0)	49 (0)	44 (3)	29 (0)
Fasting gastric volume, mL	226 ± 11	229 ± 11	247 ± 11	222 ± 12
Postprandial gastric volume, mL	736 ± 13	740 ± 14	735 ± 14	770 ± 17

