Δ postprandial fasting gastric volume, mL	511 ± 13	525 ± 12	488 ± 12	548 ± 19 ^a
Proportion of GE at 2 h	0.47 ± 0.02	0.49 ± 0.02	0.45 ± 0.02	0.42 ± 0.03
GE, T1/2, min	126.0 ± 4.4	126.8 ± 4.7	135.5 ± 5.6	137.6 ± 6.0
Satiation: maximum tolerated volume, mL	1028 ± 44	1044 ± 40	1046 ± 45	1106 ± 81
Satiation: aggregate symptom score	158 ± 14	186 ± 10	188 ± 12	184 ± 16
Colonic filling at 6 h, %	48 ± 5	54 ± 4	56 ± 3	44 ± 5
Colon transit GC 24 ^b	2.35 ± 0.16	2.03 ± 0.10	3.03 ± 0.19	2.34 ± 0.10
Colon transit GC 48 ^c	3.23 ± 0.18	3.0 ± 0.13	4.14 ± 0.17	3.94 ± 0.16
Rectal compliance, Pr _{1/2} , mm Hg	12.6 ± 0.8	12.5 ± 0.8	14.2 ± 0.6	14.0 ± 0.9
Threshold for first sensation, mm Hg	7.8 ± 0.5	7.8 ± 0.7	8.4 ± 0.7	8.1 ± 0.8
Threshold for gas, mm Hg	13.8 ± 1.5	14.0 ± 1.2	13.3 ± 1.2	14.5 ± 1.6
Threshold for pain, mm Hg	29.1 ± 2.1	29.0 ± 2.0	31.0 ± 1.8	31.0 ± 2.2
Threshold for urgency, mm Hg	17.5 ± 1.1	20.5 ± 1.6	18.8 ± 1.4	17.4 ± 1.2
Sensation rating, pain 30 mm Hg	55.1 ± 4.5	52.5 ± 4.6	55.3 ± 4.2	54.3 ± 5.6
Sensation rating, urgency 30 mm Hg	74.9 ± 2.8	71.5 ± 3.3	74.4 ± 2.5	74.3 ± 3.1

NOTE. There were 41 controls and 122 patients with IBS (data are mean ± SEM). For the number of participants undergoing each measurement, see the Methods section.

^aP = .017 versus healthy controls.

^bOverall P < .001.

^cOverall P < .001.

In a prior study that evaluated abdominal pain scores on a daily diary 0-100 mm for severity of abdominal pain, patients with IBS had the following pain severity at baseline prior to treatment (Pain, 100-mm VAS 37.2 (27.1–49.5) (57)

parameter	Mean	SD	Effect size (absolute and % of mean), 80% power; α=0.05
Average pain score on 0-100mm VAS	37.2	11	13.16 (35%)
Colonic transit GC24	3.03	1.25	1.5 (50%)
Colonic transit GC48	4.14	1.12	1.34 (32%)
Rectal compliance	14.2	3.94	4.7 (33%)
Threshold for first sensation	8.4	4.59	5.5 (65%)
Threshold for gas	13.3	7.87	9.4 (71%)
Threshold for pain	31	11.81	13.3 (43%)
Threshold for urgency	18.8	9.18	11 (59%)
Sensation rating pain 30 mmHg	55.3	27.55	33 (60%)
Sensation rating urgency 30mm Hg	74.4	16.4	19.6 (26%)
Gastric emptying T1/2	135.5	36.7	44 (32.6%)
Proportion of gastric emptying at 4h	0.45	0.13	0.156 (34.7%)

FEASIBILITY AND TIME FRAME

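### The 80%-power threshold effects for first sensation, gas and urgency are t-test figures, but the thresholds will be analysed by proportional hazards, which has less power at those effects

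*Combined protocol and SAP*

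**What the plan says.** The Sample Size section states: "The estimated effect size (with $n=12$ per treatment group) for each of the primary and secondary endpoints is based on power calculation". The table that follows it carries the column heading "Effect size (absolute and % of mean), 80% power; α=0.05" and names no test. Its threshold rows are:

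| Threshold | Mean (mm Hg) | SD | Printed effect |
|---|---|---|---|
| First sensation | 8.4 | 4.59 | 5.5 (65%) |
| Gas | 13.3 | 7.87 | 9.4 (71%) |
| Pain | 31 | 11.81 | 13.3 (43%) |
| Urgency | 18.8 | 9.18 | 11 (59%) |

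Under Statistical Analysis, B. Physiological Data, Sensation pressure thresholds, pressure takes the place of time because some thresholds will be censored. Kaplan-Meier curves describe the data, and "proportional hazards regression models will be used to assess group effects separately for each of the sensation types". The covariates of the sensory-rating models go into these models too. According to the ascending method of limits section, pressure is applied by "increasing in steps of 4 mm Hg for 1 minute per step from 0 to a maximum 60 mm Hg", so thresholds are read on a coarse grid with an upper limit.

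**The concern.** A power figure belongs to a particular test against a particular alternative. Here the effects appear to come from a comparison of means, while the group effect will be judged by a Cox coefficient. When a mean shifts and the SD stays the same, a Cox or log-rank test is generally less efficient than a t-test, and the 4 mm Hg steps add heavy ties. If the shortfall is material, a non-significant threshold result would be read against an 80% that the analysis never had. Rectal sensation by ascending limits is part of secondary aim 2 and is a listed secondary endpoint.

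**Working it through.** **1. Reproduce the printed effects.** Inputs: 12 per arm and α = 0.05 from the Sample Size section; SDs from the table. Two-sided testing is inferred, since it reproduces 11 of the table's 12 rows. With 22 degrees of freedom the noncentral t gives 80% power at a difference of 1.197 SD.

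| Threshold | 1.197 × SD | Printed | t-test power at printed effect |
|---|---|---|---|
| First sensation | 1.197 × 4.59 = 5.49 | 5.5 | 80.1% |
| Gas | 1.197 × 7.87 = 9.42 | 9.4 | 79.8% |
| Urgency | 1.197 × 9.18 = 10.99 | 11 | 80.1% |
| Pain | 1.197 × 11.81 = 14.1 | 13.3 | 75.1% |

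Three rows are t-test effects. The pain row is the one that does not reproduce. That is a separate slip, so pain is left out of the comparison below.

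**2. Power of a Cox test at the same effects, equal SDs.** The documents give no distribution, treated-arm SD, hazard ratio or censoring rate, so these are assumed. Simulation: 12 v 12; thresholds with the table's mean and SD; treated mean raised by the printed effect at the same SD; values rounded up to 4 mm Hg steps; censoring above 60 mm Hg; treatment as the only term; Efron ties; 1,200 trials per cell. The Monte Carlo standard error is √(0.68 × 0.32 / 1,200), or about 1.3 points.

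| Threshold | Normal | Gamma | Log-normal |
|---|---|---|---|
| First sensation | 70% | 64% | 64–65% |
| Gas | 72% | 63% | 67–68% |
| Urgency | 73% | 65% | 67% |

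The t-test on the same gridded data gave 77–80%. Further runs of up to 4,000 trials per case, including Weibull shapes, stayed within about 60–75%.

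**3. Sensitivity.**
- *SD rising in proportion to the mean.* Cox power is about 53–61% and t-test power about 52–62%. A smaller repeat run had its lowest Cox cells at 48% for first sensation and 52% for gas.
- *Handling of ties.* With Breslow ties and normal thresholds, power is 49% for first sensation, 61% for gas and 65.5% for urgency. The plan does not name a tie method.
- *Log-rank score test, equal SDs.* Gas and urgency give 70–77%, with simulated size of about 6–7%.

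**4. A check by formula.** Take Weibull thresholds with the table's mean and SD and the same shape in both arms, so that hazards are proportional. For gas the shape is 1.74, so HR = (13.3/22.7)^1.74 = 0.394. With 23.9 expected events, Schoenfeld power is Φ(√(23.9/4) × |ln 0.394| − 1.96) = Φ(0.32), or 62%. Urgency (HR 0.370, 23.6 events) gives 68% and first sensation (HR 0.383, 24 events) gives 65%. Reaching 80% would need 37, 32 and 35 events respectively, and the trial can supply at most 24.

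**5. Effects that an unadjusted Cox test would detect with 80% power, equal SDs.** Gas: about 10.5 mm Hg (normal) to 12 mm Hg (gamma), or 79–90% of the mean against the printed 71%. Urgency: about 12.3–13.7 mm Hg, or 65–73% against 59%.

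**The case against.** The strongest reply is that these figures do not describe the planned model. The plan puts about ten covariates (age, sex, BMI, four mood scales, two HAD scales, the somatic score) plus treatment into a model with at most 24 events. Adding ten pure-noise covariates to the simulation raised type I error to 13–15%, so power at α = 0.05 has no clear meaning there. This stands. It is a separate and larger issue, but it does not rescue the 80%: the shortfall is already present in the simplest Cox model, so cutting covariates would not restore it.

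A reader might infer that choosing the Cox test causes the whole loss, or that proportional hazards is the wrong method. The documents do not support that. The table gives one historical SD per row and says nothing about the treated arm. If the SD grows with the mean, the two tests have similar power and the shortfall comes mainly from the variance assumption. Censoring is also a sound reason for a time-to-event method.

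The consequence is also limited. The study is a declared pilot, lists small sample size as a limitation, and fixes enrolment at 24. A reader might infer that the next trial would be sized wrongly. The Significance section, however, says the next trial will be planned from the variability of response seen here, not from this table.

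**Conclusion.** The point holds as a mismatch between sizing and analysis. The first-sensation, gas and urgency effects are 80%-power effects for an unadjusted two-sided t-test at 12 per arm. At those effects an unadjusted Cox test has roughly 60–75% power under equal SDs, and about 53–61% if the SD rises with the mean. Every Cox or log-rank scenario tried fell below 80%. The direction is therefore firm, while the size rests on assumed distributions, SDs, tie handling and censoring.

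Two stronger statements should be avoided. One is that the planned analysis has some specific power: that cannot be derived from the documents, and the covariate-laden model is not what was simulated. The other is that all four threshold rows are 80% t-test effects. The pain row is not: 13.3 mm Hg has 75% t-test power, and 80% needs about 14.1 mm Hg. Priority is minor.

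**What to change.** In the Sample Size table, add a footnote saying that the threshold rows are unadjusted two-sample t-test effects and do not give 80% power for the proportional hazards analysis. Then do one of the following:

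- keep the printed first-sensation, gas and urgency effects and state power of roughly 60–75% for an unadjusted Cox test, with the assumptions shown; or
- replace them with simulated 80%-power effects for the Cox or log-rank test that will actually be used. Unadjusted and under equal SDs these are about 10.5–12 mm Hg for gas and 12–14 mm Hg for urgency.

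Correct the pain row separately. Also reconcile the row labels: the table sizes a threshold for first sensation, whereas the data-analysis and statistical sections analyse first desire to defecate, which has no row.

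The cost is a short simulation and a few table cells that look slightly less favourable. Conduct and sample size do not change.

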In addition, the investigator or designee will instruct the participant to call immediately if the selected contraception method is discontinued and document the requirement to use an alternate protocol-specified method, including if the participant will no longer use abstinence as the selected contraception method, or if pregnancy is known or suspected in the participant or partner.

Study Design

Baseline: After recruitment, consent form completion, and screening examination within 30 days of consent, eligible participants (determined after review of the 2-week run in diary) will undergo a colonic transit measurement with scans at 6-8, and 24 hours. After the 24 hr image is obtained, participants will undergo rectal compliance and sensation study. These baseline tests will take up to 2 days.

Clinical Trial: This is a prospective, randomized placebo-controlled trial of rimegepant in participants with non-constipation IBS and chronic abdominal pain where 24 have started their assigned treatment. The randomization schedule will be generated by Pfizer and communicated to the research pharmacy, with the study participants and investigators blinded. Allocation to treatment will be concealed from all participants and investigators. Randomization and delivery of study medication through the clinical research trials unit will occur after the performance of the baseline colonic transit, and rectal sensation and compliance testing. The trial period will consist of a two-week run-in period (before presenting to the clinical research trials unit for the baseline testing), and a 4-week (28-32 days) treatment period. Participants will fill a daily diary regarding abdominal pain, stool consistency and bowel function. They will also complete questionnaires that survey anxiety and depression and IBS-QOL during the screening period and at the end of the 4-week (28-32 days) trial. The final washout phase is a total of 4 weeks, during which the daily diary is continued for 28 days which includes the following questionnaires: Daily Abdominal Pain, Bloating, Flatulence, and Urgency Scores by VAS, Daily Bowel Diary including Bristol Stool Form Scale, and the Likert Scale Questionnaire for Most Intense Pain (0-4) The IBS Quality of Life Questionnaire and Hospital Anxiety Depression Questionnaire will be completed at the end of 4 weeks after the last dose of study medication.

SCHEDULE OF ASSESSMENTS

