The following measurements are derived: (i) the sensory thresholds for gas, first desire to defecate, urgency, and pain during ascending method of limits, (ii) the sensation score (gas, urgency, and pain) in response to the four phasic distensions (12, 24, 30 and 36 mmHg above BOP), and (iii) rectal compliance.

The sequential proportionate volumes (observed volume/maximum observed volume) will be used to obtain a pressure corresponding to half the maximum observed volume using a computer-based linear interpolation algorithm.⁵⁵ Thus, the summary value for each compliance curve will be calculated from the pressures corresponding to the volumes just above and just below the half maximum volume. This provides the specific pressure ($Pr\ 1/2$) corresponding to one half of the maximum observed volume, for each participant, where a smaller $Pr\ 1/2$ corresponds to higher rectal compliance.

STATISTICAL ANALYSIS

A. *Clinical Data*

- a. **Abdominal pain score:** the average pain score each day, as measured by the 100 mm VAS, over the treatment period will be calculated and compared between groups using an unpaired analysis (t test or rank sum test if not normally distributed). The averages during run-in 2-week period will be available to conduct analysis using the baseline measurement as covariates.
- b. **Clinical scales for depression, quality of life** (HADS and IBS-QOL). These summaries will be obtained from measurements made at baseline, at the end of treatment, and 4 weeks after treatment ends.

In addition to calculating these summaries, demographic and other information, including participant age and gender, as well as other medications will be recorded for each participant and summarized as appropriate for the type of data.

Treatment success for chronic pain is defined as a 30% decline in subjective pain ratings on visual analog scales for the treatment group compared to the placebo treatment group. An “Intent to Treat” data analysis will be used given the possibility that some participants will not be able to complete the study. Descriptive statistical analysis and unpaired t-tests (or rank sum test) will be used.

B. *Physiological Data*

Colonic Transit

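### The SD of 11 behind the primary-endpoint power row is not supported by the plan's only pain dispersion figure, and the 30% success line lies below the 35% that row calls detectable

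*Combined protocol and SAP*

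**What the plan says.** The Sample Size section introduces its table with "The estimated effect size (with $n=12$ per treatment group" and attributes the inputs to earlier data from the same institution (references 56 and 57). For pain it quotes a prior study's pre-treatment severity as "Pain, 100-mm VAS 37.2 (27.1–49.5" and does not say whether the limits are quartiles, a confidence interval or a range. The primary row of the table reads "Average pain score on 0-100mm VAS 37.2 11 13.16 (35" (the last figure is a percentage of the mean), under a column headed "80% power; α=0.05".

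Under Statistical Analysis, A. Clinical Data, average daily pain over the treatment period is to be "compared between groups using an unpaired analysis (t test or rank sum test if not normally distributed". Baseline adjustment appears only as a possibility: "The averages during run-in 2-week period will be available to conduct analysis using the baseline measurement as covariates". The same section adds: "Treatment success for chronic pain is defined as a 30% decline in subjective pain ratings on visual analog scales for the treatment group", relative to placebo. It does not say what the 30% is a percentage of, and no power is given for it.

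**The concern.** Every other SD in the table can be traced to the physiologic data table printed above it, which is labelled as mean ± SEM: each is close to the IBS-D standard error times √43. The pain score is not in that table. Its SD of 11 has no stated derivation and lies close to the half-width of an unlabelled, asymmetric interval.

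The SD sets the only precision figure given for the primary endpoint. If the true SD is larger, a null result could be taken as evidence against a 35% effect that the trial had much less than 80% power to detect. The success definition adds a second difficulty. It is a smaller effect than the one the table calls detectable, and it is not linked to the test or to a confidence interval, so the two criteria can give different answers on the same data.

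**Working it through.** **Inputs.** n = 12 per arm, α = 0.05, 80% power, mean 37.2, SD 11, interval 27.1 to 49.5 (Sample Size); unpaired t test and 30% success line (A. Clinical Data); run-in pain of at least 30 mm for entry (Inclusion criteria). Sidedness is not stated. Two-sided is used because it reproduces the plan's figure and one-sided does not (one-sided gives 11.53 mm).

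**1. The plan's own figure.** For a two-sided two-sample t test with 22 df (noncentral t), the detectable difference at 80% power is 1.197 × SD. With SD 11 this is 1.197 × 11 ≈ 13.16 mm, and 13.16/37.2 = 35%. Power at 13.16 mm is 79.97%. The row reproduces.

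**2. Where SD 11 might come from.** Width 49.5 − 27.1 = 22.4; half-width 11.2. Distances from the centre: 37.2 − 27.1 = 10.1 and 49.5 − 37.2 = 12.3. Mean ± SD with SD 11 would be 26.2 to 48.2, which is not the printed interval. For comparison, other rows: GC24 0.19 × √43 = 1.25; pain rating 4.2 × √43 = 27.5; gastric emptying 5.6 × √43 = 36.7.

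**3. What the interval would imply.**
- Interquartile range (assumption, roughly normal): SD = 22.4/1.349 = 16.6.
- 95% CI of a mean: SD = (11.2/1.96) × √n, with n not given. For example, n = 20 gives 25.6 and 23% power at 13.16 mm.
- Central 95% range of patients: SD = 22.4/3.92 = 5.7, detectable difference 6.8 mm, power at 13.16 mm above 99%.

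**4. Effect of the entry rule under the IQR reading.** Assume the source patients were not already selected on pain. Truncating N(37.2, 16.6) at 30 gives a baseline mean of 46.2 and SD of 11.4, a variance ratio of 0.468. With correlation ρ between run-in and on-treatment scores (not documented), the on-treatment SD is 16.6 × √(1 − 0.532ρ²).

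| Case | SD | Detectable difference (% of 37.2) | Power at 13.16 mm |
|---|---|---|---|
| Plan | 11 | 13.2 mm (35%) | 80% |
| IQR, ρ = 0.8 | 13.5 | 16.1 mm (43%) | 63% |
| IQR, ρ = 0.6 | 14.9 | 17.9 mm (48%) | 54% |
| IQR, ρ = 0.4 | 15.9 | 19.0 mm (51%) | 49% |
| IQR, no selection | 16.6 | 19.9 mm (53%) | 46% |

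**5. The 30% line.** Taken of 37.2 (assumption), it is 0.30 × 37.2 = 11.16 mm. Power of the unadjusted t test is 66% at SD 11 and 35% at SD 16.6. At SD 11, 80% power would need 17 per arm.

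**6. Success rule against test.** The smallest observed difference giving p < 0.05 is 2.074 × SD × √(2/12). That is 9.3 mm (25%) at SD 11 and 14.1 mm (38%) at SD 16.6. At SD 11, an observed difference between 9.3 and 11.16 mm is significant but misses 30%. At SD 16.6, one between 11.16 and 14.1 mm meets 30% without significance.

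**The case against.** The strongest reply is that nothing has been miscalculated and the true SD is unknown. That stands. A reader might infer an arithmetic error, but 13.16 mm is exact for SD 11. A reader might also take the half-width origin as established. It is an inference: the half-width is 11.2, and the section cites source data that may contain the SD directly.

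It is tempting to go further and say that the right figures are SD 16.6, 19.9 mm and 46% power. The documents do not support that. It requires the unlabelled limits to be quartiles and the entry rule to leave on-treatment scores unaffected. Selection on run-in pain also narrows any correlated later score, which is why the working gives a range. Nor do the documents settle the direction, since a range-type reading gives an SD well below 11.

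The 66% is likewise conditional. If the base were the truncated run-in mean of 46.2, then 30% would be 13.9 mm, with 84% power at SD 11; a lower placebo mean on treatment would shift it the other way. Adjustment for the run-in average would also help: at SD 11, power for 11.16 mm is about 78% at an assumed correlation of 0.5 and 84% at 0.6. At SD 16.6, a correlation of 0.6 gives only about 50%. The plan commits to no such adjustment and gives no correlation.

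Finally, this is a declared pilot that lists small sample size as a limitation, and it nowhere claims 80% power for 30%. That lowers the severity. It does not remove the point, because the plan still states a power figure, a hypothesis test and a success rule for its primary aim.

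**Conclusion.** The concern holds as one about an unsupported input and an unreconciled threshold. The primary row is correct conditional on SD 11, but the one pain dispersion figure in the protocol does not yield SD 11 on the readings examined. Under the IQR reading, the detectable difference is about 16 to 20 mm (43 to 53% of 37.2) and power at 13.16 mm is about 46 to 63%. This assumes approximate normality, an unselected source sample and a run-in correlation of up to 0.8. A confidence-interval reading is worse for any plausible source sample size; a range-type reading is better.

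The mismatch between 30% and 35% does not depend on how the interval is read. With 37.2 as base and SD 11, power at the success line is about 66%, and significance is reached at an observed 25%. The point should be fixed, but for a pilot it is not a reason to hold the trial.

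**What to change.** 1. State what the limits 27.1 and 49.5 are, and replace SD 11 by the SD they or the source data imply. If the source data give an SD near 11 for a population entered under the same pain rule, say so and keep it.
2. Restate the primary row over a range of SDs instead of one value, for example SD 11, 14, 16.6 and 20, giving 13.2, 16.8, 19.9 and 23.9 mm.
3. State the base of the 30% (planning mean, run-in mean or placebo on-treatment mean) and the power at the resulting difference.
4. Before unblinding, make the primary comparison the ANCOVA treatment difference adjusted for the run-in average, reported with its 95% CI. Read the 30% as a benchmark against that interval, not as a separate success rule.

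The cost is a few restated figures and a short change to the analysis text. No extra patients are needed. The drawback is that the stated precision will probably look less favourable than the current row.

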The covariates to be considered for inclusion in the ANCOVA models for colonic transit are gender, BMI, HAD scores (anxiety and depression scales), the BDQ Somatic Symptom Checklist (SSC) score. These will be considered for inclusion by checking plots of residuals (from the ANCOVA models) against these scores. The analysis will compare colonic transit between the two treatment groups.

Gastric Emptying

Given the reports of nausea and vomiting in participants with migraine as well as observations of these symptoms during clinical trials of CGRP receptor antagonists, we will also measure gastric emptying $T_{1/2}$ (minutes) and proportion emptied at 4h (%) at the end of 4 weeks treatment and compare the results for the active treatment group to those of the placebo group. Sex and BMI will be considered as co variates in this analysis.

Sensory Ratings

The assessment of phenotype associations with observed sensory ratings (rectal sensation VAS scores) will be based on analysis of covariance (ANCOVA) for repeated measures (the four phasic distension levels). Each type of VAS score will be analyzed individually (first sensation, gas, urgency, and pain). The covariates to be included in the ANCOVA models for each VAS score were age, sex, BMI, the “tiredness”, “peace”, “worried”, and “activity” VAS scores, the HAD scores, and the BDQ SSC score. Though most of these scores may not be significant covariates in these models, due to the nature of the responses, it is appropriate to include them. In addition, the corresponding pressure (12, 24, 30, 36 mmHg) at each phasic distension level (the repeated factor) is included in each of these ANCOVA models along with the main effect term for phenotype (e.g. age, sex, BMI), and the 2-way interaction term for phenotype by pressure.

Sensation pressure thresholds

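### The planning row for gastric emptying at 4 h uses 2 h data, so its 80% power statement is unsupported for that endpoint; the pain-threshold row gives about 75% power, not 80%

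*Combined protocol and SAP*

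**What the plan says.** The protocol states the gastric endpoint consistently. The Endpoints section lists "Gastric emptying of solids $T_{1/2}$ (minutes) and % emptied at 4h" as secondary endpoint c, and the Gastric Emptying paragraph of the Statistical Analysis compares the arms on "proportion emptied at 4h (%) at the end of 4 weeks treatment".

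The Sample Size section says its effect sizes cover the primary and secondary endpoints and come from IBS-D patients at the site. Its planning table has a row "Proportion of gastric emptying at 4h" with mean 0.45, SD 0.13 and effect 0.156 (34.7%). The row above it, "Gastric emptying T1/2", has mean 135.5 and SD 36.7. The pain-threshold row has mean 31, SD 11.81 and effect 13.3 (43%). The column heading gives 80% power and α = 0.05 without saying whether the test is one- or two-sided.

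The source, Table 4, has one row for the proportion emptied, "Proportion of GE at 2 h", with 0.45 ± 0.02 for IBS-D. A note says that "data are mean ± SEM".

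**The concern.** The endpoint and the label of the planning row both refer to 4 h, but the number in the row matches a 2 h measurement. If the mean and SD belong to another time point, the detectable effect and its percentage of the mean do too, and the 80% power statement does not describe the endpoint to be analysed. The protocol says the pilot will supply variance data for a later controlled trial, so a mislabelled benchmark could be carried forward.

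The pain-threshold row raises a separate doubt. Its ratio of effect to SD differs from every other row, which suggests a slip that makes the study look more sensitive on that measure than it is.

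**Working it through.** **1. Reproduce the plan's figure.** For a two-sample t-test (noncentral t, two-sided 0.05, 12 per group, 22 df), 80% power needs a standardised difference of 1.197.
- 1.197 × 0.13 = 0.1556, against 0.156 stated. 0.156 / 0.45 = 34.7%. Power at 0.156 is 80.2%.
- Alternatives fit less well: the normal approximation gives 1.144 × 0.13 = 0.149, and a one-sided t-test gives 1.048 × 0.13 = 0.136.

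The row's arithmetic is right for its inputs.

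**2. Trace the inputs.** Table 4 reports SEMs, so SD = SEM × √n. The IBS-D column shows 44 people, but the planning SDs correspond to about 43.
- 2 h proportion: 0.02 × √43 = 0.131 (stated 0.13).
- T1/2: 5.6 × √43 = 36.7 (stated 36.7; n = 44 would give 37.1).
- Pain threshold: 1.8 × √43 = 11.80 (stated 11.81).

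Mean and SD both identify the row labelled 4 h as the 2 h data.

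**3. Check 0.45 against T1/2 = 135.5 min.** For a single emptying curve:
- At 120 min: exponential 1 − 0.5^(120/135.5) = 0.459; linear 120 / (2 × 135.5) = 0.443. Both are close to 0.45.
- At 240 min: exponential 1 − 0.5^(240/135.5) = 0.707; linear 240 / (2 × 135.5) = 0.886.
- Starting instead from 0.45 at 2 h: exponential 1 − 0.55² = 0.698; linear 2 × 0.45 = 0.90.

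The assumed shapes therefore put the 4 h value at about 0.7 to 0.9.

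**4. Could a group mean still be 0.45 at 4 h?**
- From the mean and SD of T1/2 alone, Cantelli's inequality allows at most 36.7² / (36.7² + 104.5²) = 0.110 of patients above 240 min. The other 0.89 have emptied at least half, so the mean is at least 0.89 × 0.5 = 0.445. This does not exclude 0.45.
- Add the 2 h mean of 0.45, taken at face value. An equal 4 h mean would require no emptying between 2 h and 4 h, so no patient could have T1/2 between 120 and 240 min. Then (T − 120)(T − 240) ≥ 0 for every patient, and the variance is at least 360 × 135.5 − 28,800 − 135.5² = 1,619.75, an SD of about 40.2 min. The stated SD is 36.7.
- Under a normal or lognormal T1/2, only 0.2% to 1.1% of patients would exceed 240 min.

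**5. Effect on the detectable difference.** The absolute effect depends on the SD and n; the percentage also depends on the mean.
- If the SD stayed at 0.13, the effect would stay 0.156, or 0.156 / 0.90 = 17% to 0.156 / 0.70 = 22% of the mean, not 34.7%.
- Simulating T1/2 as normal or lognormal (mean 135.5, SD 36.7) with exponential to steeper emptying curves gives 4 h means of about 0.72 to 0.87 and SDs of 0.09 to 0.12. The effect is then about 0.11 to 0.145, or 15% to 17% of the mean.
- An SD of 0.15 would give 1.197 × 0.15 = 0.180.

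These are illustrations, not replacement figures.

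**6. Pain-threshold row.** The other eleven rows have effect/SD ratios of 1.193 to 1.200 and power of 79.7% to 80.2%. This row has 13.3 / 11.81 = 1.126 and power of 75.1%. The consistent value is 1.197 × 11.81 = 14.1 mmHg, and 14.1 / 31 = 46% (to the nearest whole per cent). The normal approximation does not rescue it: power at 13.3 is then 78.8%, while the other rows rise to about 83%.

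**The case against.** The strongest reply is that little depends on this row. The trial is a declared pilot with 12 per group, no sample size was derived from the row, and the formula was applied correctly. All of that stands. The fault is a mislabelled input, and it touches one component of one of eight secondary endpoints.

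Several stronger readings are tempting, but the documents do not support them:

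- *That T1/2 alone makes 0.45 impossible at 4 h.* This is strict for one curve, but the bound for a group mean is about 0.445. The 2 h value or an ordinary distribution of T1/2 is also needed, so implausible is the right word.
- *That power for the 4 h endpoint is overstated.* If the 4 h SD is below 0.13, then 0.156 is conservative. No 4 h SD is given.
- *That the effect would run into the ceiling.* An increase of 0.156 exceeds 1.0 only if the mean is above 0.844, and only for faster emptying. A decrease fits anywhere in the range, and the plan names no expected direction for gastric emptying.
- *That nausea and vomiting would be interpreted against the wrong figure.* The Gastric Emptying paragraph plans a direct comparison of arms. Nothing says the result will be judged against 0.156.
- *That power is claimed for a threshold the trial does not collect.* The planning table has a first-sensation row, while the ramp section says "Thresholds for gas, first desire to defecate, urgency, and pain are indicated by the study participants". Both lists have four thresholds, so this may be only inconsistent naming. It needs reconciling, no more.

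On the pain threshold, it is fair to say that the planned analysis is Kaplan-Meier and proportional hazards with censoring. The 75% corrects the table on its own t-test basis; it is not the power of the planned test.

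**Conclusion.** The point holds as a table error with two parts.

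First, the row labelled 4 h holds 2 h data. The match of mean and SD to Table 4 needs no outside source. The stated 80% power to detect 0.156 (34.7%) is unsupported for the 4 h endpoint. The 34.7% is very probably wrong, since it uses a mean of 0.45 where assumed shapes suggest about 0.7 to 0.9. The direction of the error in the absolute effect is unknown.

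Second, the pain-threshold effect should read 14.1 mmHg (46%), not 13.3 (43%). At 13.3 the power is about 75%, assuming a two-sided t-test, which the other eleven rows fit.

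Neither part changes the sample size, the primary endpoint or the planned analyses.

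**What to change.** - Keep the 4 h endpoint, which the Endpoints and Gastric Emptying sections state consistently. Either replace the row's mean, SD and detectable effect with sourced 4 h data, or relabel the row as 2 h data for information and withdraw the 80% power statement for the 4 h endpoint. Do not move the endpoint to 2 h to suit the row: that is a substantive endpoint change, and the text supplied lists no 2 h image.
- Restate the pain-threshold row as 14.1 mmHg (46%), with a note that it rests on a t-test while the planned analysis is proportional hazards.
- State in the column heading that the test is two-sided.
- As a minor point, reconcile first sensation (the planning table and the VAS list under Sensory Ratings) with the sensations actually collected under the ascending ramp and the phasic distensions. Do not carry the first-sensation figures over to first desire to defecate; Table 4 has no data for that threshold.

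The cost is a few table and wording edits, plus locating a 4 h data source if the first option is taken. One stated figure, the pain threshold, becomes slightly less favourable.
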